STUDY NUMBER: **UCCI-BRAIN-16-01**

STUDY TITLE: Feasibility Study of Modified Atkins Ketogenic Diet in the Treatment of Newly Diagnosed Malignant Glioma

PRINCIPAL INVESTIGATOR: [name]
Adjunct-Associate Professor of Medicine
Division of Hematology/Oncology
[name]
[name]
[contact]
[contact]
[contact]

CO- INVESTIGATORS

[name], RD, CSO, LD
Clinical RD, Specialist in Oncology Nutrition
University of Cincinnati Cancer Institute
[name]
[name]
[name]
[contact]
[contact]
[contact]

STATISTICIAN:

[name]
Research Associate Professor of Psychiatry
Department of Psychiatry and Behavioral Neuroscience
University of Cincinnati Academic Health Center
[name]
[name]
[contact]
[contact]
[contact]

SUPPORT: UC Brain Tumor Center [name] Endowed Chair Fund

AGENT: Temozolomide

SCHEMA:

1. Diagnosis of High Grade Glioma (-28 days)
2. Pretreatment Visit 1: Meet with Physician and/or Nurse Practitioner (NP) for chemotherapy teaching. (day -28 to day -7)
 - a. Check lipid profile, complete metabolic panel, complete blood count with differential (CBC with diff), and hemoglobin A1C
 - b. Take medical history concerning pancreatitis, recent cholecystectomy or gallbladder dysfunction, diabetes, dairy allergies and/or lactose intolerance, in-born errors of metabolism
 - c. Obtain informed consent
 - d. Obtain tissue from biopsy or resection
3. Pretreatment Visit 2: Meet with Nurse Practitioner for chemotherapy teaching (day -28 to day -7)
 - a. Laboratory Correlatives
 - i. Serum beta-hydroxybutyrate (BHB)
 - ii. Complete metabolic panel, fasting serum glucose and insulin
 - iii. Vital signs, height, body weight, waist circumference
 - iv. Platelet mitochondrial labs
 - v. Neurocognitive testing (See Appendix VI)
 - vi. Quality of Life (FACT-Br) survey (See Appendix I)
 - vii. MRI planning scan
4. Pretreatment Visit 3: Meet with registered RD (RD) for nutritional education concerning carbohydrate restricted diet (Modified Atkins Diet (MAD)) (day -28 to day -7)
 - a. Diet education consultation with RD – 1.5 hours. Distribute week 1 food diary with education concerning completion (Appendix II)
 - b. Confirm above histories and labs
 - c. Random assignment to MAD ketogenic diet with radiation therapy day -7
5. Radiation/Chemotherapy commences (Day 0-Day 42)
 - a. Collect daily food diaries
 - b. Weekly visits with NP/MD
 - i. Serum BHB
 - ii. Complete metabolic panel, fasting serum glucose and insulin levels
 - iii. Vital signs, body weight, waist circumference
 - iv. Quality of Life (FACT-Br) survey (See Appendix I)
 - c. Weekly telephone contact with RD to address diet related concerns
6. Radiation and temozolomide treatment terminated
 - a. Continued MAD until MRI (Day 43-70)
7. MRI and post-treatment visit #1 (approximately Day 70)
 - a. Meet with RD

- i. If patient wishes to discontinue research diet, RD will instruct patient on 3-day titration back to pre-study carbohydrate intake levels.
- ii. If patient wishes to continue longer term discuss supplement use to prevent nutritional deficiencies from long-term diet.
- b. Meet with attending physician
 - i. Review MRI findings
 - ii. Review post-intervention maintenance chemotherapy
 - iii. Laboratory Correlatives
 - i. Lipid profile, complete metabolic panel, complete blood count with differential (CBC with diff), and hemoglobin A1C
 - ii. Serum BHB
 - iii. Fasting serum glucose and insulin
 - iv. Vital signs, body weight, waist circumference
 - v. Platelet mitochondrial Labs
 - iv. Adverse Events
 - v. Performance Status
 - vi. Quality of life (FACT-Br) survey (See Appendix 1)
 - vii. Neurocognitive testing (See Appendix VI)
- 8. MRI and Ppost-treatment visit #2 (approximately day 126-154 after post-treatment MRI)
 - a. Meet with attending physician
 - i. Review MRI findings
 - ii. Review post-intervention maintenance chemotherapy
 - iii. Laboratory Correlatives
 - i. Lipid profile, complete metabolic panel, complete blood count with differential (CBC with diff) and hemoglobin A1C
 - ii. Serum beta-hydroxybutyrate
 - iii. Fasting serum glucose and insulin
 - iv. Vital signs, body weight, waist circumference
 - v. Platelet Mitochondrial Labs
 - iv. Performance Status
 - v. Quality of life (FACT-Br) survey (See Appendix 1)
 - vi. Neurocognitive testing (See Appendix VI)

[figure not shown]
1. OBJECTIVES

- 1.1. Hypothesis/Rationale of the Study: Modified Atkins diet (MAD) concurrent with radiation therapy will produce ketosis and improve outcomes in patients with malignant gliomas due to increased sensitivity of the tumors to radiation therapy.
- 1.2. Primary Objectives
 - 1.2.1. Assessment of feasibility of inducing ketosis with MAD concurrent with radiation therapy by measuring serum beta-hydroxybuterate
 - 1.2.2. Assessment of fasting glucose and insulin levels with MAD concurrent with radiation therapy
 - 1.2.3. Assessment of compliance with MAD concurrent with radiation therapy
- 1.3. Secondary Objectives
 - 1.3.1. Assessment of 6-month progression-free survival in patients with high-grade gliomas with MAD concurrent with radiation therapy as compared to historical controls
 - 1.3.2. Safety of MAD concurrent with radiation and chemotherapy therapy
- 1.4. Exploratory Objectives
 - 1.4.1. Assessment of QOL changes with MAD concurrent with radiation therapy
 - 1.4.2. Assessment of cognitive function changes with MAD concurrent with radiation therapy
 - 1.4.3. Assessment of 2-year survival of patients with high-grade primary brain neoplasms with MAD concurrent with radiation therapy as compared to historical controls
 - 1.4.4. Assessment of mitochondrial respiration in peripheral platelets and correlate with cognitive findings

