3. STUDY DESIGN

- 3.1. This is a single arm feasibility study.
- 3.2. Study Diet: Patients will be screened for study eligibility and written informed consent will be obtained prior to enrollment. Patients will meet with the registered dietitian (RD) one to four weeks prior to initiation of concurrent radiation and chemotherapy. At that visit, the RD will provide education on all aspects of MAD including meal planning and daily food diary completion (Appendix II). The diet will begin approximately 7 days prior to the initiation of concurrent radiation and chemotherapy and the patient will continue the study diet until the first post-radiation MRI, a time period of approximately 10 weeks. We will obtain blood to assess serum BHB, fasting insulin and glucose, and other chemistries as well as body weight weekly, according to the standard of care, while on chemotherapy and radiation therapy. Participants will receive weekly phone calls from the RD to address any questions or concerns the patient may have regarding the MAD and daily food diary. A food diary (Appendix II) will be used to assess adherence during the 10-week period. All macronutrient intake from food diaries will be entered by study agent into nutrient analysis software. This macronutrient breakdown will be utilized to identify potential problematic macronutrient intake which may be preventing patient from achieving ketosis. This is available online as well.
 - 3.2.1. Temozolomide and radiation will be given according to the standard protocol described by Stupp et al.ⁱ Patients will receive 75 mg/m² of temozolomide concurrent with radiation therapy at standard dose. The dose of radiation and/or chemotherapy and/or steroid may be modified by the attending physician based on clinical indications.
 - 3.2.2. Correlative platelet mitochondrial studies will be drawn on the pre-treatment visit #2, the post-treatment visit #1 and the post-treatment visit #2. Patients are already having blood drawn at these visits as standard of care. This sample will be transported within 6 hours to the laboratory **[name] at Cincinnati Children's Hospital Medical Center** for assessment of mitochondrial respiration in the platelets.
 - 3.2.3. QOL studies will be done at the pre-treatment visit #2, pre-treatment visit #3, weekly during chemotherapy and radiation, at the post-treatment visit #1 and then at post-treatment visit #2

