7. DOSING DELAYS / DOSE MODIFICATIONS

- 7.1. If serum ketosis is not obtained (BHB ≥ 0.5 mM), the RD will review the daily food diary (Appendix II) to determine if the calculation of net carbohydrate intake is accurate and to modify the diet to obtain ketosis.
- 7.2. If patient develops Grade 3 or Grade 4 toxicity determined to be related to the diet then patient will be removed off diet. Toxicity can be determined by research coordinator, primary investigator or co-investigator.
- 7.3. If patient has a fasting glucose level >90 mg/dl, it will precipitate an evaluation of dietary intake and/or medical issues (i.e. infection).
- 7.4. If patient is admitted to the hospital while on study/diet, compliance with the diet will be up to the admitting physician and the patient. If the admission is secondary to the diet/protocol, this will be documented as a serious adverse event and the diet will be discontinued to till patient returns to Grade 1 level and then the diet can be resumed. If the patient has a second serious adverse event from the protocol, then the patient will be permanently removed from the diet. Please see section 6.2

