10.2. Definitions

10.2.1. **Quality of Life (QOL)**: QOL will be assessed using the FACT-Br QOL tool. See Appendix I. QOL scores pre-intervention will be compared to post intervention-QOL score. QOL will also be obtained at the post-treatment visit #2 to assess if termination of intervention decreased QOL score. We understand that there are many variables that can affect QOL during this time other than the intervention.

10.2.2. **Two-year survival (2YS)**: Duration of survival will be defined as the number of months from diagnosis to death due to any cause.

10.2.3. **6-month progression free survival (6moPFS)**: will be defined as the percentage of patients without progression (defined below) at 6 months.

10.2.4. **Ketosis**: Will be defined as serum BHB ≥ 0.5 mM

10.2.5. **Compliance**: Dietary adherence is assessed by review of the daily food diary (Appendix II) serum ketone levels.

10.3. **Methods for Evaluation of Measurable Disease**: All baseline evaluations should be performed as closely as possible to the beginning of treatment. MRI imaging techniques that can be used to determine progression are:

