10.4.1.3. Clear progression of non-measurable disease

10.4.1.4. Any new lesion

10.5 Statistics

10.5.1 Ketosis will be defined as serum BHB > 0.05 mM throughout 6-week period of radiation and chemotherapy. We hope to find that in our given sample of 30 patients at least 50% will meet this criteria. We will compute a 95% confidence interval for this rate to estimate the likely range in the target population. A 10% increase in glutamate within the tumor on the post-RT MRI as compared to the pre-RT MRI will be considered evidence that the tumor is using ketones as fuel by the conversion to glutamate.

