APPENDIX VIII

Modified Ketogenic Diet Guidelines

The modified ketogenic diet (MKD) is a diet that reduces the amount of carbohydrates you eat so that your body will begin burning primarily fat, instead of carbs, for energy. This diet is very low in carbohydrates, high in fat and moderate in protein.

When your body breaks down the carbohydrates found in food it makes a product called glucose. Glucose, commonly known as blood sugar, is the main source of energy for the body. The focus of the ketogenic diet is to shift your metabolism to use fat as the main source of energy. When your body breaks down fat it makes products known as ketones. When your body is using ketones for energy it is said that you are in “ketosis”.

The goal of this diet is to get your body into ketosis and keep it there. Your doctor will monitor your level of ketosis by checking your blood for ketones. This will help you and your team know if you are following the diet properly. You may also monitor yourself via urine Ketostix. Your dietitian will explain their use.

Some individuals lose weight when they start this diet. It will be important to monitor this because it can indicate loss of lean muscle mass as well as loss of crucial vitamins and minerals important to maintaining your energy throughout treatment.

The guidelines below are designed to help you be successful in acquiring and maintaining ketosis.

1. Eat either three regular-sized meals per day or four to five smaller meals. Do not skip meals or go more than six waking hours without eating.
2. Eat no more than 20 grams of NET carbs per day. Try to eat a wide variety of vegetables including lettuce-based salads. This will help you get more vitamins and minerals for overall health, but also fiber needed to feel full longer and aid in preventing constipation. Remember, carb counts of various vegetables are different so be sure to check them. Use measuring cups, measuring spoons, and food scales for measuring all foods to ensure accuracy.
3. At each meal, including breakfast, eat 4 to 6 ounces of protein foods, including poultry, beef, lamb, pork, veal, fish and shellfish, eggs, and cheese; you may count 1 egg as 1 ounce of protein. There is no need to trim fat from meat or the skin from poultry, but it is fine if you prefer to. Just add a splash of olive or avocado oil or a pat of butter to your meal to replace the fat.

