4. There is no restriction on fat. Enjoy butter, olive and avocado oils, canola oil, and seed and nut oils and mayonnaise. Aim for 1 tablespoon of oil on a salad or other vegetables, or a pat of butter. Cook foods in just enough oil to ensure that they don't burn. Or spritz the pan with a mist of oil.
5. Use spices and herbs to flavor foods. Get creative with meals and snacks to keep interest in the food you are eating. You will be given resources to find recipes appropriate for your diet.
6. This diet can cause constipation. Make sure you drink plenty of water, eat all of the recommended salad greens and vegetables, and let your doctor and/or dietitian know if you are becoming constipated. Occasionally, a medication bowel regimen is necessary.
7. Cheese can be a good source of fat and protein; however, cheeses such as cottage and ricotta have higher net carbs, so please remember to measure these carefully. Also, cheese can cause constipation – limit your daily intake to 4 ounces or less.
8. Acceptable sweeteners include sucralose (Splenda), saccharine (Sweet'N Low), stevia (SweetLeaf or Truvia). Have no more than three packets a day and count each one as 1 gram of carbs. These sweeteners themselves contain no carbs; however, the fillers they are packaged with to prevent caking do contain a little bit of carbohydrates. If you purchase a bulk container of these sweeteners, check the nutrition facts label for net carb content; they are not all the same.
9. To satisfy your sweet tooth you can have sugar-free gelatin desserts. There are resources for recipes within this educational packet that will give you more ideas.
10. Each day, drink at least eight 8-ounce portions of approved beverages: water, club soda, herb teas, or coffee (caffeinated in moderation). This will prevent dehydration and electrolyte imbalances. In this count, you may include two cups of broth (not low sodium), one in the morning and one in the afternoon.
11. Don't starve yourself and don't skimp on fats.
12. Don't assume that any food is low in carbs. Always read the labels on packaged whole foods being certain to note the serving size.

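### Section 10.5.1 scores ketosis on BHB alone, so the rate cannot separate ketosis on the MAD as taught from ketosis sustained partly by poor intake; add a supplementary rate that takes intake into account

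*Combined protocol and SAP*

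**What the plan says.** Section 1.2.1 gives the first primary objective as "Assessment of feasibility of inducing ketosis with MAD concurrent with radiation therapy by measuring serum beta-hydroxybuterate". The scoring rule is in section 10.5.1: "Ketosis will be defined as serum BHB > 0.05 mM throughout 6-week period of radiation and chemotherapy". The target follows: "We hope to find that in our given sample of 30 patients at least 50% will meet this criteria". A 95% confidence interval is promised, without a method. Section 10.2.4 defines ketosis again, also by BHB only but at another cut-off: "Will be defined as serum BHB ≥ 0.5 mM".

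Diet and intake are covered elsewhere:

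- Section 3.2 has patients keep a food diary, uses it to assess adherence, and adds: "All macronutrient intake from food diaries will be entered by study agent into nutrient analysis software". The stated use of that breakdown is to find what stands in the way of ketosis.
- Section 7.1 sets the ketone-related trigger: "If serum ketosis is not obtained (BHB ≥ 0.5 mM), the RD will review the daily food diary".
- Section 10.2.5 judges compliance from the diary and serum ketones, with no cut-off. Compliance is a separate primary objective (1.2.3).
- Section 8.2.1 lists food refusal and nausea among the diet's possible adverse effects.
- Appendix VIII explains: "When your body breaks down fat it makes products known as ketones". It tells patients not to skip meals, and guideline 11 says: "Don't starve yourself and don't skimp on fats".

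**The concern.** The objective asks whether the MAD can bring about ketosis, but the score records only that ketosis was present. The protocol itself names a second source. It attributes ketones to fat breakdown, expects that some patients may refuse food or feel sick, and gives the diet alongside temozolomide and radiation. A patient who eats little departs from the diet as taught, yet can pass the BHB criterion.

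The trial has a single arm, so no comparison group shows how much ketosis poor intake alone produces during chemoradiation. The ketone-related diary review looks in one direction only: it starts when ketosis is absent, and no rule asks what lies behind ketosis when it is present. What is at stake is how the main feasibility figure is read. Poor tolerance of the diet, which argues against feasibility, could add to the rate offered as evidence for it.

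**Working it through.** **1. The plan's own figure.** There is no sample-size formula, null rate or power statement to reproduce. The only figure is the target, 15/30 = 50%. Its 95% CI is 31.3 to 68.7% (Clopper-Pearson), 33.2 to 66.8% (Wilson) or 32.1 to 67.9% (Wald).

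**2. What each rule requires.**

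| Place | BHB | Intake or weight condition |
|---|---|---|
| 10.5.1 | > 0.05 mM for the whole 6 weeks | none |
| 10.2.4 | ≥ 0.5 mM | none |
| 10.2.5 (compliance) | serum ketones, no cut-off | diary review, no cut-off; no link to the ketosis count |

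Both ketosis definitions ignore intake. Compliance is not an independent check, because it uses ketones itself.

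**3. Effect per patient.** With 30 patients, each one counted through poor intake adds 1/30 = 3.3 points. The BHB rule cannot remove a patient who is ketotic on the diet, so the error through this route has one sign.

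**4. Range of effect.** Suppose 15/30 is observed and k of the 15 were sustained partly by poor intake. The documents do not give k, so the values are assumptions, starting at zero. Exact limits are the 2.5% point of Beta(x, 30 − x + 1) and the 97.5% point of Beta(x + 1, 30 − x), with x = 15 − k.

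| k | Diet-attributable rate | Exact 95% CI |
|---|---|---|
| 0 | 15/30 = 50.0% | 31.3 to 68.7% |
| 1 | 14/30 = 46.7% | 28.3 to 65.7% |
| 2 | 13/30 = 43.3% | 25.5 to 62.6% |
| 3 | 12/30 = 40.0% | 22.7 to 59.4% |
| 5 | 10/30 = 33.3% | 17.3 to 52.8% |

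**5. Chance of reaching the hoped-for rate.** Let d be the true diet-induced rate and q the share of the remaining patients who are ketotic through poor intake (assumed). The rate that is scored is p = d + (1 − d)q. For d = 40% and q = 10%, p = 0.40 + 0.60 × 0.10 = 0.46. The binomial probability of at least 15 successes in 30 is:

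| d | q = 0 | q = 5% | q = 10% | q = 20% |
|---|---|---|---|---|
| 30% | 1.7% | 4.5% | 10.1% | 31.5% |
| 40% | 17.5% | 27.6% | 39.7% | 65.7% |
| 50% | 57.2% | 67.7% | 76.9% | 90.3% |

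For d = 40%, q = 10% means 30 × 0.60 × 0.10 = 1.8 patients on average.

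**6. The cut-off.** The two thresholds differ by 0.5/0.05 = 10 times. Every patient at or above 0.5 mM is also above 0.05 mM, so the lower cut-off can only give an equal or higher rate and is less specific to the diet.

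**The case against.** A reader might infer that the plan is blind to under-eating. It is not. Weight is recorded weekly during chemoradiation, the dietitian telephones weekly, diaries are daily and serve to assess adherence, and adverse events are collected. Section 6.1.2 expects early weight loss and allows energy intake to be adjusted. Under-eating would be seen; it simply does not enter the ketosis count.

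A reader might also infer that an under-eating patient would be scored adherent on carbohydrate alone. No such score exists. Compliance rests on review of the diary, and a dietitian facing a near-empty diary need not call it adherent.

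Third, 10.5.1 requires ketosis for the whole six weeks, so a short fast cannot create a success. This limits the problem but does not remove it: a patient ketotic on the diet early and through poor intake later still qualifies.

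Fourth, the 50% is a hope attached to an estimate, not a go/no-go rule, and feasibility also rests on compliance, glucose and insulin. The documents therefore do not support saying that the trial would declare the diet feasible because patients had stopped eating.

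Fifth, section 2.2 treats caloric restriction as a possible contributor to tumour control, and section 6.1 sets no numeric energy minimum for the MAD. Ketosis at low intake is thus not plainly a failure under the hypothesis. This, with the reliance on diaries kept by patients or caregivers, is a good reason not to replace the BHB endpoint. It does not answer objective 1.2.1, which concerns ketosis produced with this diet.

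**Conclusion.** The gap in the scoring rule is certain: under either definition, ketosis counts whatever sustains it, and no planned analysis separates the sources. The diet-attributable rate can be overstated by this route but not understated, at 3.3 points per affected patient. The size is unknown and may be zero. The counts k and shares q above are assumptions that show sensitivity, and they predict nothing about this trial. Any statement that a particular number of the 30 will be ketotic from poor intake goes beyond the documents.

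The point limits how the primary rate can be read and does not invalidate it. It calls for a supplementary analysis, with the primary definition kept. The conflict between > 0.05 mM in 10.5.1 and ≥ 0.5 mM in 7.1 and 10.2.4 comes first, because the count of ketotic patients is undefined until those passages are reconciled.

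**What to change.** 1. Reconcile the ketosis threshold across 7.1, 10.2.4 and 10.5.1 before any rate is computed.
2. Keep the BHB rate as the primary rate and name the exact (Clopper-Pearson) interval.
3. Add to 10.5.1 a supplementary rate with an exact 95% CI: patients who are ketotic and whose diary energy intake meets an analysis floor. The study dietitian fixes the floor before outcome data are seen. Show the rate also at one lower and one higher floor, since the MAD has no energy minimum of its own.
4. Report weeks with missing diaries separately and do not count them as failures. Judge each patient on the weeks available. Show a ketotic patient with no usable diary as unclassified, leave that patient out of this rate's denominator, and state the number.
5. Tabulate diary intake and weekly weight change for all ketotic patients.
6. State in advance that the feasibility conclusion will be qualified if the two rates differ materially, and say what difference counts as material.

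The cost is a paragraph in 10.5.1, one derived variable and one table. Energy follows from the macronutrient data already entered under 3.2, and weights are already taken weekly. The floor is a scoring rule and changes no patient care. The downside is that diaries are self-reported and may understate intake, so the supplementary rate can itself run low; this is another reason to keep it supplementary.
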